Duration of response	= Date of first progression or death after initial response - date of first response + 1 Date of disease progression is defined as the date of imaging showing disease progression. Date of response is defined as the first date of imaging showing CR or PR. If no progression or death is observed after initial response, the duration of response will be censored at the last date of tumor assessment.
Duration of CR	= Date of first progression or death after initial response - date of first CR + 1 Date of disease progression is defined as the date of imaging showing disease progression. Date of CR is defined as the first date of imaging showing CR. If no progression or death is observed after initial CR, the duration of CR will be censored at the last date of tumor assessment.
Other variables	
Overall survival (OS)	Date of death – date of randomization + 1 If no death is observed, OS will be censored at the last date known to be alive.
Time to treatment failure (TTF)	Date of treatment discontinuation for any reason (including disease progression) as assessed by investigator, treatment toxicity, patient preference, or death) – date of randomization If no treatment discontinuation is observed, TTF will be censored at the date of last study treatment.
Body surface area (BSA)	$BSA [m^2] = \text{SQRT}((\text{weight [kg]} \times \text{height [cm]}/3600))$
Number of combination treatment cycles	Number of treatment cycles with full combination treatment (3 doses of CetuGEX™/cetuximab, one dose of cisplatin/carboplatin, 4 doses of 5-FU) Only cycles in which all planned medication has been given will be counted as a full cycle. Dose reductions will however not prevent a cycle to be counted as full.
Overall treatment duration [weeks]	(Date of last treatment administration – date of first treatment administration) + 1 for CetuGEX™/cetuximab
Treatment duration [weeks] during combination treatment	(Date of last treatment administration within a combination cycle – date of first treatment administration) + 1 for CetuGEX™/cetuximab
Treatment duration [weeks] in maintenance phase	(Date of last treatment administration – date of first treatment administration after last Day 15 administration in combination treatment phase) + 1 for CetuGEX™/cetuximab

Total doses [mg]	Sum of actual doses administered for CetuGEX™/cetuximab cisplatin/carboplatin and 5-FU
------------------	--

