## **9.2 Secondary Efficacy Analysis**

Secondary efficacy analyses will be based on the ITT and PP population.

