### ***9.2.2 Tumor Response Rates***

ORR and CBR according to different criteria (irRC, RECIST) and sources (investigator, central review) will be analyzed using Chi-square tests to evaluate the effects of treatment on ORR and CBR for the combination treatment period as wells for the entire treatment period including maintenance treatment. 95%-confidence intervals will be calculated for the rates and their treatment differences based on normal approximation.

Logistic regression models will be used to investigate the influence of the stratification factors on the response variables. These models will include the treatment effect and the randomization stratification factors. The odds ratios, the corresponding 95% confidence intervals and the p-values of the Wald test will be presented for all factors.

Absolute and relative frequencies of tumor response categories will be tabulated by time point and for the best response. Waterfall plots to illustrate individual maximum percentage change of target lesion size form baseline will be presented by treatment group.

Duration of response will be analyzed by Kaplan-Meier methods. Duration of CR will be described case by case.

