14.2.10.1	ITT, PP	Clinical Benefit Rate (Independent Centralized Reading Based on RECIST 1.1) Frequencies, Chi-Squared Test and Confidence Intervals	16.2.6.2
14.2.10.2	ITT, PP	Clinical Benefit Rate (Independent Centralized Reading Based on RECIST 1.1) Logistic Regression Model	16.2.6.2
14.2.10.3	ITT, PP	Clinical Benefit Rate (Investigator Assessment Based on irRC) in FcγRIIIa-allotype Subgroups - Primary Definition Frequencies and Confidence Intervals	16.2.6.3
14.2.10.4	ITT, PP	Clinical Benefit Rate (Investigator Assessment Based on RECIST 1.1) in Tumor Location Subgroups - Primary Definition Frequencies and Confidence Intervals	16.2.6.3
14.2.10.5	ITT, PP	Clinical Benefit Rate (Investigator Assessment Based on RECIST 1.1) in Recurrence Subgroups - Primary Definition Frequencies and Confidence Intervals	16.2.6.3
14.2.10.6	ITT, PP	Clinical Benefit Rate (Investigator Assessment Based on RECIST 1.1) in EGFR treatment subgroups - Primary Definition Frequencies and Confidence Intervals	16.2.6.3
14.2.11.1	ITT, PP	Duration of Response (Investigator Assessment) Log-Rank Test and Kaplan-Meier Analysis	16.2.6.3
14.2.11.2	ITT, PP	Duration of Response (Independent Centralized Reading based on irRC) Log-Rank Test and Kaplan-Meier Analysis	16.2.6.3

Table Number	Population	Table Title / Summary	Supporting Listing
14.2.11.3	ITT, PP	Duration of Response (Independent Centralized Reading based on RECIST 1.1) Log-Rank Test and Kaplan-Meier Analysis	16.2.6.3
14.2.12.1	ITT, PP	Time to Treatment Failure Log-Rank Test and Kaplan-Meier Analysis	16.2.6.3
14.2.12.2	ITT, PP	Time to Treatment Failure Cox Proportional Hazards Model	16.2.6.3
14.2.13.1	ITT, PP	Overall Survival Log-Rank Test and Kaplan-Meier Analysis	16.2.6.3
14.2.13.2	ITT, PP	Overall Survival Cox Proportional Hazards Model With Stratification Factors	16.2.6.3
14.2.13.3	ITT, PP	Overall Survival in FcγRIIIa-allotype Subgroups Kaplan-Meier Analysis	16.2.6.3
14.2.13.4	ITT, PP	Overall Survival in Tumor Location Subgroups Kaplan-Meier Analysis	16.2.6.3
14.2.13.5	ITT, PP	Overall Survival in Recurrence Subgroups Kaplan-Meier Analysis	16.2.6.3
14.2.13.6	ITT, PP	Overall Survival in EGFR treatment subgroups Kaplan-Meier Analysis	16.2.6.3
14.2.13.7	ITT, PP	Overall Survival – Stratification Factors and Second Line Treatment Cox Proportional Hazards Model	16.2.6.3
14.2.14.1	ITT, PP	Progression Free Survival (Investigator Assessment) – Landmark Analysis Log Rank Test and Kaplan-Meier Analysis	16.2.6.3

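### The planned log-rank test of duration of response compares responders only, so its p-value, shown under an ITT, PP label, is not a valid test of a treatment effect on duration

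*SAP*

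**What the plan says.** SAP 15.1 lists three tables for duration of response, each for the ITT and PP populations:

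- Table 14.2.11.1: "Duration of Response (Investigator Assessment) Log-Rank Test and Kaplan-Meier Analysis"
- Table 14.2.11.2: "Duration of Response (Independent Centralized Reading based on irRC) Log-Rank Test and Kaplan-Meier Analysis"
- Table 14.2.11.3: "Duration of Response (Independent Centralized Reading based on RECIST 1.1) Log-Rank Test and Kaplan-Meier Analysis"

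The derivation in SAP 7.2 is "Date of first progression or death after initial response - date of first response + 1", and "Date of response is defined as the first date of imaging showing CR or PR". The only censoring rule is "If no progression or death is observed after initial response, the duration of response will be censored at the last date of tumor assessment". A patient who never responds gets no value. The rule in SAP 7.1 that treats patients without sufficient data as failures covers response and benefit rates only.

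The methods text is narrower than the table list. SAP 9.2.2 says "Duration of response will be analyzed by Kaplan-Meier methods" and names no test. SAP 9.2 adds "Secondary efficacy analyses will be based on the ITT and PP population". By contrast, SAP 9.2.1, 9.2.3 and 9.2.4 each name a log-rank test, for central-read PFS, time to treatment failure and OS. Protocol 7.1.2 lists duration of response as a secondary endpoint, but protocol 13.4.3.2 assigns it no test. SAP 12 declares no departure from the protocol.

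**The concern.** An ITT label tells a reader that the randomized groups are being compared. Here they are not: treatment helps decide who responds, so the two sets of responders need not be alike at baseline even though the arms are. Stratifying by FcγRIIIa balances the arms, not the responders. Protocol 5.3 expects CetuGEX to be active in FF and FV patients, in whom cetuximab shows little ADCC activity, so responders could well differ by genotype between arms.

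Short responses can also enter easily. The SAP derivation requires no confirmation of response, and scans are six weeks apart to Week 18. A response first seen at Week 6 and lost at Week 12 counts as 42 + 1 = 43 days, or 43/30.4375 = 1.4 months. If lost at Week 18 it counts as 84 + 1 = 85 days, or 2.8 months.

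At stake are six between-arm p-values (three reads in two populations) that could be read as evidence that one drug gives longer or shorter responses.

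**Working it through.** **No plan figure to reproduce for this endpoint.** The documents give no response rate, responder count, alpha or power for duration of response. The only sizing is for PFS: medians 5.6 and 8.4 months, two-sided 0.05, 80% power, 192 events. Schoenfeld's formula gives 4 × (1.960 + 0.842)² / (ln 0.667)² = 191, so that figure stands. It supplies two inputs here: about 240/2 = 120 patients per arm, and a planned median ratio of 8.4/5.6 = 1.5.

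**Set-up.** Trials of 120 per arm were simulated, 3000 to 4000 runs per case. Assumptions not in the documents:

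- 36% of patients respond on either drug (shared responders), with control median duration 6 months.
- CetuGEX adds 0, 10 or 20 percentage points of responders.
- Durations are exponential, with censoring uniform between 10 and 34 months.

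The log-rank test is applied to responders only: z = (O − E)/√V, ln HR ≈ (O − E)/V, significant if |z| > 1.96. An HR above 1 counts against CetuGEX. The nominal rate of a significantly worse result is 2.5%.

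**Check with no added responders.** HR 0.99 and two-sided rejection 5.9%, so the test behaves when there is no selection.

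**Added responders with short responses:**

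| Added responders | Shared responders 6 vs 6 months (no duration effect) | Shared responders 6 vs 9 months (planned ratio) |
|---|---|---|
| +10 points, median 3 months | HR 1.13 | HR 0.80, worse in 0.2% |
| +20 points, median 3 months | HR 1.22, worse in 16% | HR 0.92, worse in 1.1% |
| +10 points, median 2 months | HR 1.18 | HR 0.85, worse in 0.2% |
| +20 points, median 2 months | HR 1.33, worse in 28% | HR 0.99, worse in 1.8% |

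Across repeat runs the middle column spans HR 1.12 to 1.33, with a significantly worse result in about 9% to 28% of trials, although no patient does worse on CetuGEX. In the right column the true HR in shared responders is 6/9 = 0.67 and the apparent HR is 0.80 to 0.99, so the benefit is diluted.

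**Added responders as durable as the rest (median 6 months, no duration effect).** HR 0.99, worse in 2.2% to 2.5%: no distortion.

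**Wider range of assumptions.** Shared response rate 25% to 45%, shared median 5.6 months in both arms, 10 to 20 points added at 2 to 3 months: HR 1.10 to 1.39, significantly worse in 6% to 29%, significantly better in under 1%.

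**One case in closed form** (shared 35%, added 15 points at 2 months):

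- The CetuGEX responders are a mixture with weight 0.35/0.50 = 0.7. Solving 0.7 × 2^(−t/5.6) + 0.3 × 2^(−t/2) = 0.5 gives a median of 4.0 months, against 5.6 in control.
- Mean time in response per randomized patient is 0.35 × 5.6/ln 2 = 2.83 months in control and (0.35 × 5.6 + 0.15 × 2)/ln 2 = 3.26 months on CetuGEX.

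The responders-only summary falls while the all-patient summary rises.

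**The case against.** **The direction is not established.** A reader might infer that if CetuGEX works as planned, this test will count against it. The documents do not support that. The plan is a 1.5-fold gain in median PFS. When that ratio is carried over to shared responders, a significantly worse result is rarer than the nominal 2.5% in all four cases. An apparent reversal needs no duration effect in shared responders, together with added responders whose responses last a half or a third as long. Nothing in the documents shows that added responders would be short-lived. Long-lived added responders, or an arm that responds only in good-prognosis patients, would push the bias the other way. This objection stands.

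**The test may be leftover template text.** The table list has visible copying errors: numbers 14.2.16.1 to 14.2.16.7 are used twice, and blocks for central reading carry investigator titles. With 9.2.2 silent on a test, the log-rank wording may not be intended. That is plausible, but the tables are what will be programmed, so the text and the list must be aligned either way.

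**The tables will not stand alone.** SAP 13.2 says the sizes shown with summary statistics count patients with non-missing values, so responder numbers should be visible. ORR on the full denominator and ITT PFS are also reported. This reduces the risk of misreading but does not make the p-value a randomized comparison.

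**Conclusion.** The concern holds. The log-rank test in Tables 14.2.11.1 to 14.2.11.3 compares groups selected after randomization, and its p-value is not a valid test of a treatment effect on duration. That conclusion needs no simulation: it follows from the definition in SAP 7.2.

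The size and sign of the bias do rest on assumptions. Depending on how long added responders stay in response and whether shared responders gain duration, the test can make a harmless arm look worse, mask a real benefit, or show no distortion. The stronger claim that the better arm will be penalized is not supported.

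Severity is minor to moderate. Duration of response is one of several secondary endpoints, no alpha or decision rule depends on it, and the primary ITT analysis of PFS is unaffected.

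**What to change.** Delete the log-rank test from Tables 14.2.11.1 to 14.2.11.3, which brings them into line with SAP 9.2.2. Keep the Kaplan-Meier estimates by arm and label the tables *responders in ITT/PP, descriptive*, with the number of responders per arm in the column header. The cost is a change of SAP and table wording.

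Optionally, if a between-arm comparison is wanted, add one measure over all randomized patients: mean time in response up to a fixed horizon (12 months, for example), non-responders at zero, with a 95% confidence interval. It can be derived from data already planned for Listing 16.2.6.3. The SAP would need to state the horizon and the censoring rule, including how new anticancer treatment is handled, since the primary PFS derivation has such a rule and duration of response has none. This addition is not needed to cure the defect.

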---------------------	---

	
each analysis level, a patient will be counted only once. Frequencies for TEAE will also be given for causality and severity graded according to Common Toxicity Criteria (NCI-CTC; AE criteria Version 4.0). In addition, toxicity as evaluated via incidence of AEs will be analyzed by Fc-gamma receptor allotype subgroups (FF, FV, VV) The incidences of ADA will be summarized in frequency tables per treatment arm.
 
For biomarkers as well as hematology and biochemistry laboratory variables, descriptive summaries of observed values and changes from baseline will be presented by treatment arm. The assessments of laboratory variables concerning reference ranges and clinical relevance will be tabulated by visit for each clinical laboratory parameter by treatment arm (frequency tables). Additionally, for each laboratory parameter, shifts in assessments from baseline to the last on-study value will be presented by treatment arm (shift tables).
 
Descriptive summaries of observed values and changes from baseline will be calculated for vital signs. These summaries will be presented by visit and treatment arm.
 
Descriptive summaries of observed values and changes from baseline will be calculated for ECG variables. QT will be corrected according to Bazett. Frequency and shift tables will be presented for the classified values of QT_c as given by the International Conference on Harmonisation (ICH)-E14, as well as for the overall clinical assessment.
 
Finding in post-baseline physical examinations will be documented as AE and analyzed as part of the general AE analysis.

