13.4.4.4 Electrocardiograms and Echocardiograms

Descriptive summaries of observed values and changes from baseline will be calculated for ECG variables. QT will be corrected according to Bazett. Frequency and shift tables will be presented for the classified values of QT_c as given by the International Conference on Harmonisation (ICH)-E14, as well as for the overall clinical assessment.

For ECHO/MUGA assessments, descriptive values of observed values at baseline (“Normal”/“Abnormal [not] clinically significant”) will be presented by treatment arm.

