### 10.4 Electrocardiogram

The summary ECG assessment (categories: normal, abnormal – not clinically significant, abnormal – clinically significant) will be tabulated by visit (frequency tables). Additionally, shifts in assessments from baseline to EOS visit will be presented by treatment arm (shift tables).

Descriptive summaries of actual values and changes from baseline will be presented for ECG measures of PR interval, QRS interval, QT interval, QTc interval (Bazett), and HR (heart rate) by visit and treatment arm.

If not available in the clinical database, Bazett's Correction (QTcb) will be derived as follows:

$$\text{Bazett's Correction (QT}_{c_b}\text{)} \quad \text{QT}_{c_b} = \frac{QT_{msec}}{\sqrt{RR}}$$

where: Relative Rate:  $RR = 60 / \text{HR}$   
HR = heart rate obtained from ECG.

Also, the number and percentage of patients in each treatment group with QTc values 451 - 480 ms, 481 - 500 ms or >500 ms and the number and percentage of patients in each treatment group who experienced a change >30 ms or a change >60 ms will be presented by visit.

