## **12. CHANGES COMPARED TO THE CLINICAL TRIAL PROTOCOL**

All planned statistical analyses are in agreement with the clinical trial protocol.

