14.3.4.1.2	Safety	Laboratory Data – Hematology and Biochemistry Changes from Baseline by Visit	16.2.8.1 – 16.2.8.2
14.3.4.1.3	Safety	Laboratory Data – Hematology and Biochemistry Assessment of Abnormalities by Visit	16.2.8.1 – 16.2.8.2
14.3.4.1.4	Safety	Laboratory Data – Hematology and Biochemistry Shift in Assessment of Abnormalities from Baseline to Last Combination Therapy Visit	16.2.8.1 – 16.2.8.2
14.3.4.1.5	Safety	Laboratory Data – Hematology and Biochemistry Shift in Assessment of Abnormalities from Baseline to Last Visit	16.2.8.1 – 16.2.8.2
14.3.4.1.6	Safety	Laboratory Data – Hematology and Biochemistry CTC Grade by Visit	16.2.8.1 – 16.2.8.2
14.3.4.1.7	Safety	Laboratory Data – Hematology and Biochemistry Shift in CTC Grade at Baseline to Maximum Post-Baseline CTC Grade	16.2.8.1 – 16.2.8.2
14.3.4.2.1	Safety	Laboratory Data – Urinalysis Assessments by Visit	16.2.8.3
14.3.4.2.2	Safety	Laboratory Data – Urinalysis Shift in Assessments from Baseline to End of Study	16.2.8.3
14.3.5.1.1	Safety	Vital Signs Data Absolute Values by Visit	16.2.9.4
14.3.5.1.2	Safety	Vital Signs Data Changes from Baseline by Visit	16.2.9.4
14.3.5.2.1	Safety	Electrocardiogram (ECG) Data Summary Assessment by Visit	16.2.9.5

Table Number	Population	Table Title / Summary	Supporting Listing
14.3.5.2.2	Safety	Electrocardiogram (ECG) Data Shift in Summary Assessment from Baseline to End of Study	16.2.9.5
14.3.5.2.3	Safety	Electrocardiogram (ECG) Data Absolute Values by Visit	16.2.9.5
14.3.5.2.4	Safety	Electrocardiogram (ECG) Data Changes from Baseline by Visit	16.2.9.5
14.3.5.2.5	Safety	Electrocardiogram (ECG) Data Classification of QTc Intervals by Visit	16.2.9.5
14.3.5.2.6	Safety	Electrocardiogram (ECG) Data Classification of QTc Interval Changes from Baseline by Visit	16.2.9.5
14.3.5.3.1	Safety	ECOG Performance Status Assessments by Visit	16.2.9.6
14.3.5.3.2	Safety	ECOG Performance Status Shift in Assessments from Baseline to End of Study	16.2.9.6
14.3.5.4.1	Safety	Exposure (CetuGEX™/cetuximab) Number of Cycles, Number of Infusions, Treatment Duration and Total Dose	16.2.5.1
14.3.5.4.2	Safety	Exposure (CetuGEX™/cetuximab) Dose Changes, Dosing Delays, Dosing Interruptions and Infusion Rate Changes (Per Patient)	16.2.5.1
14.3.5.4.3	Safety	Exposure (CetuGEX™/cetuximab) Dose Reductions, Dosing Delays, Dosing Interruptions and Infusion Rate Changes (Per Administration)	16.2.5.1

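### The SAP omits the QTc-class shift table that the protocol plans, and its by-visit QTc tables cannot give a per-patient count

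*SAP*

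**What the plan says.** Protocol 13.4.4.4 states: "Frequency and shift tables will be presented for the classified values of QT_c as given by the International Conference on Harmonisation (ICH)-E14", and extends the same sentence to the overall clinical assessment. The synopsis makes the same commitment. Neither says whether the shift runs to the last or the worst on-study value.

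SAP 10.4 tabulates the summary ECG assessment (normal, abnormal but not clinically significant, abnormal and clinically significant) by visit and adds a shift from baseline to the EOS visit for that assessment. For QTc it defines value classes of 451-480, 481-500 and above 500 ms. It then says that these classes and the patients who "experienced a change >30 ms or a change >60 ms will be presented by visit".

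The table list in SAP 15.1 matches. Table 14.3.5.2.2 is the only ECG shift table and covers the summary assessment. Table 14.3.5.2.5 is titled "Classification of QTc Intervals by Visit", and Table 14.3.5.2.6 does the same for changes from baseline. For laboratory grades, by contrast, Table 14.3.4.1.7 is a "Shift in CTC Grade at Baseline to Maximum Post-Baseline CTC Grade".

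SAP 12 reads: "All planned statistical analyses are in agreement with the clinical trial protocol".

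**The concern.** There are two separate points.

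The first is a mismatch between documents. The protocol names two objects for shift tables, the QTc classes and the overall assessment, and the SAP delivers one. A reader who relies on SAP 12 would not know that anything had been left out.

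The second concerns what the planned tables can show. For QTc the useful safety summary is how many patients per arm ever had a large value or a large rise, and from what baseline class. A by-visit table counts a patient afresh at each visit. Its rows cannot be added, because the same patient may recur, and a single row understates the total if different patients are affected at different visits. The summary-assessment shift does not fill the gap. It uses an investigator category with no millisecond threshold, and it ends at the EOS visit, so it can miss a transient excursion.

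**Working it through.** The documents give no figure to reproduce. The check is a comparison of texts, followed by a bound and an illustration.

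**1. Protocol against SAP**

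| ECG item | Protocol 13.4.4.4 | SAP 10.4 and 15.1 |
|---|---|---|
| Overall (summary) assessment | Frequency and shift | By visit (14.3.5.2.1); shift to EOS (14.3.5.2.2) |
| QTc classes | Frequency and shift | By visit (14.3.5.2.5); no shift |
| QTc change above 30 or 60 ms | Not named separately | By visit (14.3.5.2.6) |
| Observed values and changes | Descriptive | By visit (14.3.5.2.3, 14.3.5.2.4) |

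No ECG table uses a maximum or an any-post-baseline value.

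**2. What by-visit counts determine**

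Let x_v be the number of patients above 500 ms at visit v, and N the number in the arm. Over the tabulated visits, the number ever above 500 ms satisfies

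max(x_v) ≤ ever ≤ min(N, Σ x_v).

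The lower end applies when the same patients recur, the upper end when no patient appears twice. The tables cannot show where between the two the truth lies. The same holds for rises above 60 ms.

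**3. Illustration**

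Inputs from the documents:
- 240 patients randomised 1:1, so 120 per arm (protocol 13.2).
- ECGs on Day 1 of Cycles 3 and 5 and every 6 weeks thereafter (protocol 10.1.4 and 18.1), plus the Safety Visit (protocol 10.1.5).
- Planning medians for PFS of 5.6 and 8.4 months (protocol 13.2); 30.4375 days per month (SAP 7.2).

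Assumptions not in the documents: median PFS stands in for time on treatment, every patient has all k ECGs, and the chance p of exceeding 500 ms is the same at each ECG.

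Number of ECGs:
- 5.6 × 30.4375 / 7 = 24.4 weeks: weeks 6, 12, 18, 24 and the Safety Visit, so k = 5.
- 8.4 × 30.4375 / 7 = 36.5 weeks: weeks 6, 12, 18, 24, 30, 36 and the Safety Visit, so k = 7.

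Percentage of patients ever above 500 ms: p if the same patients recur; 1 − (1 − p)^k if ECGs are independent; kp if no patient appears twice.

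| p per ECG | k | Same patients recur | Independent | No patient twice |
|---|---|---|---|---|
| 0.5% | 5 | 0.5% | 2.5% | 2.5% |
| 0.5% | 7 | 0.5% | 3.4% | 3.5% |
| 1% | 5 | 1% | 4.9% | 5% |
| 1% | 7 | 1% | 6.8% | 7% |
| 2% | 5 | 2% | 9.6% | 10% |
| 2% | 7 | 2% | 13.2% | 14% |

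At p = 1% in an arm of 120, each visit row shows about 1.2 patients. That is compatible with 1.2 to 6.0 patients ever above 500 ms at k = 5 (independence: 120 × 0.0490 = 5.9) and with 1.2 to 8.4 at k = 7 (independence: 120 × 0.0679 = 8.2).

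**The case against.** The sponsor can fairly say that little is at risk. Protocol 10.3.6.2 requires clinically relevant ECG abnormalities to be reported as adverse events. SAP 10.1 counts each patient once per Preferred Term, also by maximum CTC grade (Table 14.3.1.3.1). Listing 16.2.9.5 holds the ECG data by patient, so the count could be derived. Table 14.3.5.2.6 still compares QTc with baseline; what is missing is the class-to-class cross-tabulation. The phase 1 summary in protocol 5.2 mentions no QT finding, QTc is not among the adverse events of special interest in SAP 10.1.3, and the ECG summaries are descriptive. All of this stands and keeps the point minor. None of it supplies the missing shift table, and the adverse event tables do not apply the 500 ms or 60 ms thresholds.

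Stronger readings are tempting, but the documents do not support them:
- A reader might infer that the protocol promised a worst-value or ever-exceeded count. It did not. It leaves the endpoint of the QTc shift open, and its laboratory shifts (13.4.4.2) run to the last on-study value. A baseline-to-last QTc shift would also miss a transient value above 500 ms. The missing table and the missing patient count are therefore separate matters.
- A reader might take 4.9% to 6.8% as the size of a hidden signal. It is only the independence case under an assumed rate; recurrence in the same patients gives about 1%.
- A reader might suppose that a patient with one value above 500 ms looks normal at every other visit. The intermediate classes mean that each ECG is shown in whatever class it falls.

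**Conclusion.** The point holds as a minor reporting gap. The mismatch rests on the text alone: the protocol plans a QTc-class shift table, the SAP has none, and SAP 12 is inaccurate on this item. That by-visit tables do not fix the per-patient count follows from arithmetic and needs no assumption about rates. How far the two can differ does depend on assumptions: at 1% per ECG with 5 to 7 ECGs, anything from about 1% to 5-7% of patients fits the same visit rows. The documents give no QTc rate or within-patient correlation to narrow this. Efficacy conclusions, sample size and significance level are unaffected.

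**What to change.** - Add a QTc-class shift table by treatment arm. Because the protocol leaves the endpoint open, define it in the SAP as baseline class against maximum post-baseline class, the approach of Table 14.3.4.1.7.
- Add one any-post-baseline row to each of Tables 14.3.5.2.5 and 14.3.5.2.6, counting each patient once by worst QTc and by largest increase. Show the number of ECGs or the exposure per arm beside it, since an ever-exceeded count grows with the number of ECGs. A fixed window such as the first 18 weeks is optional and would not fully equalise exposure, because patients who stop early still have fewer ECGs.
- Correct SAP 12: record how the shift endpoint was defined or, if the table is not wanted, declare its omission.

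The cost is one extra table and two extra rows from data already collected.
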